11. RECRUITMENT AND PROCEDURES PREPARATORY TO RESEARCH

Phase 1: Qualitative Interviews

We will recruit a total of 30 stakeholders to participate in qualitative interviews. Of the 30 participants, 20-25 will be military personnel with CLBP and/or CNP and 5-10 will be clinicians who provide yoga or other clinical care to military

personnel with CLBP or CNP. Of the 20-25 participants with CLBP/CNP, we will enroll at least 8-10 participants who have not done yoga before to explore reasons or perceived barriers to yoga participation. Recruitment will primarily occur through the posting of flyers and word of mouth with our military and community partners. A full Military IRB approval is not required to post flyers at the military facility or to conduct qualitative interviews at community locations off-base. Once we obtain permissions from the appropriate Public Affairs Office for the base, we will post flyers on military bases. For the 5-10 instructors/healthcare providers, we will recruit using connections with our military/community partners, and if needed, our contacts with additional healthcare providers in the San Diego area including UCSD and VA San Diego. Participants will receive a \$30 gift card for participating in a qualitative interview.

Phase 2: Yoga Classes

(Please note: before we begin Phase 2 we will also need to obtain IRB approval from NMCS D for activities that will take place at that site. Once we obtain IRB approval from NMCS D, we will provide a copy to UCSD's IRB prior to commencing any activities at that site.)

Recruitment for Phase 2 will occur primarily through our military and community partners. However, we will use qualitative interview data to steer and refine our recruitment methods. The NMCS D is our military research partner and they provide care to over 100,000 active-duty military personnel each year. With an estimated 25% of the general population having chronic low back pain at any one time, and higher rates among military personnel, the pool of potential participants can safely be placed at over 20,000. Some will not meet study criteria for various reasons, but a large number will be eligible. Once military IRB approval is obtained, [name] and staff can post the study flyer and information on a research opportunities website, request inclusion in widely distributed e-mails, notify primary care physicians, pain management staff, and other healthcare providers, and they can post flyers on medical center posting boards. Recruitment will also occur at Yoga Oceanside and through the Connected Warriors organization. Flyers will be posted within their facilities and announcements will be at the end of classes. They will both use social media (e.g. Facebook) to communicate these research opportunities to their communities (CW has 1600+ followers, and Yoga Oceanside has 500+). If needed, the study will also advertise the study in local military newspapers including three online publications from Echo Media (Miramar Flight Jacket, Navy Compass, Camp Pendleton Scout) which have a weekly readership of 88,000 and/or the Military Press publication (bi-weekly readership of over 100,000 active-duty military).

12. INFORMED CONSENT

Prior to participation in this project, participants will be thoroughly apprised of study considerations and will undergo an informed consent process. We will emphasize the key elements of the informed consent procedure: 1) the research status of the study; 2) the prospect of physical or psychological risk and the provisions for it; 3) the lack of guarantee of benefit from participation; 4) the confidentiality of the participant's responses; 5) the voluntary nature of the study; and 6) the freedom to withdraw from the study or to refuse to answer specific questions at any time. Only individuals who consent to all study conditions will be enrolled. The participant will complete the informed consent process with the RA and will be given a copy of the signed document for his or her records.

Trained research staff, who are experienced in recruitment for clinical trials and medical research, will facilitate the consenting for the qualitative interviews in Phase 1 and before the screening appointments in Phase 2. Prior to beginning the study, the PI will ensure compliance with IRB requirements and protections by obtaining approval from University of California San Diego and the Naval Medical Center San Diego (for procedures done at that facility) and will insure all protections are followed.

13. ALTERNATIVES TO STUDY PARTICIPATION

The alternative to participation is not to participate.

14. POTENTIAL RISKS

In the focus groups of Phase 1, research staff will explore the thoughts, experiences, and opinions of participants with respect to CLBP and yoga as a treatment for CLBP. They will also discuss perceptions of different aspects of a yoga intervention regarding their desirability, acceptability, and efficacy, none of which are anticipated to produce negative emotional reactions. However, participants will be given contact information for sources of help that they can contact if they are feeling distressed or desire help.

Phase 2 will involve participants attending two different yoga programs. Minor physical risks are always possible in yoga classes, although the frequency of injury has been low for CLBP and CNP patients in major studies. A small possibility also exists for injury during the physiological assessments, where someone may be asked to stand on one foot, hold a plank position, bend forward, or squeeze a dynamometer. In the event that someone is injured, the usual procedure followed at that particular facility will be followed. For example, active-duty military doing yoga at NMCS D will receive care at NMCS D. Participants doing yoga through Yoga Oceanside and the Connected Warriors program can get free care through UCSD. These organizations require instructors to be fully insured through the Yoga Alliance.

Summary of safety information. Like other exercise activity, the risks of injury from improperly performing yoga postures vary depending on how, where, and with whom the yoga is practiced. The initial practice of yoga under the direction of experienced yoga instructors, following a program that has modifications for people with limitations, and consulting a physician before starting a yoga program are all recommendations²⁴ that will be followed in the proposed study. Data from RCTs of yoga for adults with CLBP reveal that the 3 serious adverse events among 309 persons doing yoga in these studies were all related to herniated discs, and at least one of these was found to be unrelated to yoga practice.^{22,23,102,103} Disc problems are common in this population in the absence of yoga practice, and thus yoga does not appear to greatly increase that risk. Among the 63 people with CNP who did yoga in two RCTs, no serious adverse events occurred. So despite popular media reports of the dangers of yoga, no specific data or evidence of risk has been presented. The poses specifically cited as being dangerous, usually head and shoulder stands and their variations probably do present some risk for novices, and are not being used in the proposed study. By screening out patients at greater risk, placing emphasis on slowly building a safe yoga practice, and hands on instruction from experienced instructors will be used to ensure that the yoga is practiced in the safest possible manner throughout the study.

In both Phase 1 and Phase 2, there is a risk of loss of confidentiality. No physical, legal, or social risks are anticipated as a result of participating in other phases or aspects of this study. The assessment questionnaires ask participants to consider and/or report health symptoms and functioning, and medication use which are not anticipated to cause negative emotional reactions. However, participants in each phase of the study will be given contact information for sources of help that they can contact if they are feeling distressed or desire help.

15. RISK MANAGEMENT PROCEDURES AND ADEQUACY OF RESOURCES

All participants will be provided the Principal Investigator's and Project Coordinator's phone numbers, whom they can contact if they have questions or need assistance. All participants are made aware that they can discontinue participation at any time. The PI and program staff will assist the participant in obtaining a referral to a mental health professional if requested or indicated. Risks to subject confidentiality will be addressed by identification of subject information only through code numbers: Data stored in the computer will only be identified with a code number. A separate file with corresponding identifying information and contact information will be kept in a separate computer file that will be password protected. Only the appropriate research staff will have access to specific subject information.

Adverse events: The investigators will track adverse events and report these on a daily basis to the Principal Investigator. Serious adverse events will be immediately reported by phone and in writing to the IMC and to the Institutional Review Board of the University of California San Diego, or relevant military IRB. Serious adverse events include death, substantial risk of dying, hospitalizations, disability, or emergency medical intervention attributable to participation in the study (<http://www.fda.gov/medWatch/report/DESK/advevnt.htm>). We will conduct weekly research team meetings. Once a month at these research team meetings, all adverse events occurring over the previous month and over the course of the study will be reviewed. Serious adverse events will be reviewed immediately and reviewed again at the monthly meeting. All reported adverse events will be reported to the IRBs at that site as well as the University of California San Diego IRB, which will be the primary IRB of the study.

Additional precautions: Any adverse events or protocol deviations by the PI or research assistant will be reported within 72 hours of its coming to the PI's attention. We will take regular precautions to protect human research participants during the course of the study. The investigators will be in regular contact on a daily or weekly basis by e-mail or phone so urgent problems will be addressed in a timely manner. The PI or other key personnel will inform the PI or research team about any vacation or absences so that coverage of study duties can be arranged.

If this study is funded and carried out, we will assemble an Independent Monitoring Committee (IMC) to monitor the progress and safety of the study as it proceeds. The PI will recruit 3 content or scientific experts who are not involved with this grant to serve on the IMC. One person will be a clinical psychologist or psychiatrist who specializes in diagnosing and treating psychological disorders among active-duty military; another will be an orthopedist or orthopedic surgeon; the third will be a statistician. The IMC will review the study protocol prior to activation and develop an IMC plan. The IMC will evaluate the data on an ongoing basis and assure participant safety and study integrity. The IMC will be responsible for monitoring data and for making recommendations based on the data regarding appropriate protocol and any operational changes. The committee will meet every 6 months to review progress, preliminary data, and any adverse events. They will meet with the PI to make recommendations regarding the progress of the study and will be able to report to the Institutional Review Board of the University of California San Diego. Following review, the IMC will write a report outlining recommendations. These recommendations will be forwarded to the Principal Investigator ([name]) at the University of California San Diego and the IRB Chair at the University of California San Diego.

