Recruitment staff will meet with participants to obtain informed consent and HIPAA authorization before a screening visit. Potential participants will undergo a physician screening exam to ensure they meet the study inclusion/exclusion criteria and can participate safely. Screening will be performed by [name] at NMCSO or by [name] at UCSO for the community site and includes a review of the patients’ medical record, a brief interview, and a physical examination. Inclusion/ exclusion criteria and the sources of information used to determine them are listed in Table 4. Patients who have recently changed any professionally-delivered pain treatment (e.g., medications, chiropractic) are not eligible until their treatment has been stable for 30 days. Participants are asked to keep all pain treatments stable during the 12-week intervention period unless a change is medically necessary and their agreement and study participation are documented in their medical record. Staff will assess all treatments including non-prescription medication use and any treatment changes that do occur through self-report assessment at 4-weeks, 8-weeks, and the end of the 12 week study period. Participants are asked take their lowest usual dose of pain medications within 24 hours of each assessment. Although we will exclude those with serious or unstable psychiatric illness, we expect to enroll many patients with stable levels of depression, anxiety (including PTSD), substance use, etc. as these conditions are prevalent and contribute to disability among CLBP/CNP patients. Research suggests that yoga has beneficial effects on psychiatric symptoms. We will exclude patients who report active suicidal ideation at baseline or have recent suicide attempts.

Assessments and Randomization:

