All eligible participants will be scheduled for assessments at two time points: pre (baseline) and post intervention (12-weeks). The assessments consist of a battery of 8-10 questionnaires taking about 20-30 minutes to complete. Next, physiological measurements will be conducted by a trained research assistant and will take about 10 minutes to complete. Participants will receive \$30 for completing each assessments. Completed questionnaires will be coded with a study ID to protect confidentiality. All personal health information will be entered into a password protected secure server environment within UCSD-HSRC. After the baseline assessment, participants will be randomized to either the Hatha Yoga Intervention or to the Restorative Yoga Intervention. Randomization will occur through a web portal linked to a secure file providing block randomized digits that was prepared by the study statistician. There will be one block file for each site, with 30 digits in each file, allowing each site to have a balanced randomization. Research staff will not have access to the randomization file. Participants will be told of their group assignment and will be allowed to ask additional questions at that time.

Assessment Questionnaires and Measurements:

Screening: Medical record information will be used by screening physicians to complete the Back Pain History Questionnaire which will allow the investigators to assign a descriptive diagnosis based on the Quebec Nomenclature on Activity Related Spinal Disorders¹⁰⁴. The measure has been used in previous VA studies¹⁰⁵⁻¹⁰⁷. Additional information on co-morbid diagnoses, opioid pain medication usage, and ongoing treatments will also be collected including information on TBI, PTSD and other psychological diagnoses, and substance use.

Demographics: A brief questionnaire will assess age, gender, education, race/ethnicity, employment status, military rank and duties, and combat status.

Pain interference with daily function and pain severity will be measured with the short version of the Brief Pain Inventory (BPI).¹⁰⁸ Pain interference will serve as the primary outcome. The BPI has been validated with CLBP.¹⁰⁹ The pain interference score is the mean of the 7 interference items. The pain severity score is the mean of 4 severity items. The BPI has good reliability (alpha 0.77 - 0.91).

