Disability/Physical Function. The Roland-Morris Disability Questionnaire consists of 23 questions that ask about limitations experienced for a variety of daily activities. The scale has been shown to be reliable and is well validated¹¹⁰. It has been used in other studies of yoga studies¹⁰². The Neck Disability Index will be used to assess disability related specifically to neck pain. It is a well validate measure.¹¹¹

Depression. Derived from the full Center for Epidemiologic Studies Short Depression Scale¹¹² (CES-D), the CES-D 10¹¹³ consists of 10 items on the frequency of mood symptoms. Scores ≥ 10 indicate depression.

Anxiety. The Brief Anxiety Inventory (BAI) measures the severity of anxiety symptoms and consists of 21 items. The BAI was developed with psychiatric outpatients¹¹⁴ and has good reliability and validity.¹¹⁵

HRQOL. The Short-form 12 (SF12) was derived the SF-36.¹¹⁶ The PCS-12 and MCS-12 have been shown to be similar to the SF36 levels of precision and sensitivity to change.

Self-efficacy. Self-efficacy for managing pain reflects confidence in the ability to influence the intensity or impact of CLBP/CNP on daily life. The questions are based on items developed by Lorig et al.¹¹⁷.

Fatigue. The Fatigue Severity Scale (FSS) assesses the impact and severity of fatigue with 9 items. A score of ≥ 4.0 constitutes severe fatigue.¹¹⁸ The measure has good psychometrics for pain disorders.^{118,119}

Attendance/ Home practice. Attendance of yoga sessions will be assessed using sign-in logs verified by the yoga instructor. Self-reported practice of yoga at home will be assessed using a weekly participant yoga log. The yoga log assesses the amount of time practiced, the use of instructions, the difficulty of poses, and the estimated level of exertion.

Acceptability and Satisfaction Questions. We will assess program acceptability and satisfaction using 10 questions developed and used by the investigators in previous and current yoga studies. The questions will gauge factors affecting attendance and participation levels.

Patient Expectations will be measured at baseline to determine whether the descriptions of the yoga interventions could result in different expectations for improvement. [name] will use the new patient expectation measure developed by her and her colleagues.¹²⁰

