The HY intervention will be led by a certified instructor at each site. Both instructors will be trained by [name] who has been practicing yoga for over 16 years and has over 8 years of teaching experience and is the main instructor for [name] for Vets with CLBP. (NOTE: We will model the HY intervention after the current Yoga for CLBP intervention which is a classical hatha yoga with influences from Viniyoga and Iyengar yoga. Both Viniyoga and Iyengar yoga styles emphasize modifications and adaptations including the use of props such as straps and blocks in order to minimize the risk of injury and make the poses accessible to people with health problems and limitations.) The certified yoga instructors will lead participants through a series of 23 yoga poses (32 total variations) at a slow-moderate pace. Instructors will be asked to follow the manual which will help standardize the yoga intervention. The manual contains pictures and a description of how to perform each pose with typical instructor dialogue. The dialogue may be paraphrased and varied slightly, yet promotes more consistent replication and generalization of results. The manual includes some poses that could aggravate back conditions if they are not modified for some people. That is why multiple modifications are shown and many of the poses shown are only worked up to after weeks of practice and individual attention from the instructor. The more challenging poses are not included in the home practice manuals. The importance of attending all sessions will be stressed during session 1 and throughout all sessions. Participants who miss a session without notifying the instructor will be contacted to check on the reason for non-attendance. Participants will also receive a home practice manual containing some basic, safe postures that can be performed in 10-15 minutes on days they will not be attending the formal in-person sessions. Participants will be encouraged to not push themselves as much when practicing at home and to stop when pain or discomfort becomes noticeable. They will be encouraged to consult with the instructor individually before and after

class about any problems or difficulties they are encountering at home or in the formal sessions.

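### Adverse events are to be tracked, but no scheduled contact is described as asking about them, and two routes by which problems could surface are written only for the hatha arm

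*Combined protocol and SAP*

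**What the plan says.** **After an event is known.** Section 15 says: "The investigators will track adverse events and report these on a daily basis to the Principal Investigator". It adds monthly team review, immediate reporting of serious events, and reporting to the IRBs. The Independent Monitoring Committee (IMC) looks at adverse events every six months.

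**How an event becomes known.** Section 15 names no question, form or schedule. The route it gives to all participants is: "All participants will be provided the Principal Investigator's and Project Coordinator's phone numbers, whom they can contact if they have questions or need assistance".

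**Scheduled data collection (Section 9).**
- Treatment self-reports: staff will record treatments, non-prescription medication and "any treatment changes that do occur through self-report assessment at 4-weeks, 8-weeks, and the end of the 12 week study period".
- Main assessments: "All eligible participants will be scheduled for assessments at two time points: pre (baseline) and post intervention (12-weeks"). These consist of outcome scales, baseline expectations and physical measures.
- Weekly log: "The yoga log assesses the amount of time practiced, the use of instructions, the difficulty of poses, and the estimated level of exertion".
- Acceptability items: "The questions will gauge factors affecting attendance and participation levels".

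**By arm.** Under Hatha Yoga, on problems met at home or in class: "They will be encouraged to consult with the instructor individually before and after" class. The same paragraph provides for contact with anyone who misses a session without notice, to learn why. The Restorative Yoga text contains neither provision. It says that the details of that intervention, its instructor manual and its home practice manual are still to be developed.

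**The concern.** The plan is specific about handling events once they are known and silent about finding them. A serious event may well reach the team through medical care. A non-serious one, such as a strain or a flare of neck pain after home practice, may not. It would be recorded only if the participant chose to mention it, or if someone recognised it behind an indirect signal.

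The plan itself expects some harm of this kind. Its hatha section acknowledges that certain poses could aggravate back conditions if not modified, and Section 14 accepts that minor physical risks exist in any yoga class.

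Two things are at stake. The monthly review, the IMC and the IRBs can act only on events that are recorded. And Sections 14 and 18 rest their safety case on event counts from earlier yoga studies, so this pilot's counts can be expected to serve the same purpose for the planned R01 trial. A count that is too low, or shaped by which arm was invited to speak up, would be a poor basis for that.

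**Working it through.** The documents state no adverse event rate and no safety sample size, so there is no figure to reproduce. The check is a reading of each described contact, followed by an illustration.

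**1. Contacts as described in Sections 9 and 15**

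| Contact | Arms | Described content | Adverse event or injury item described? |
|---|---|---|---|
| Self-report, weeks 4, 8, 12 | Both | Treatments, medication, treatment changes | No; indirect signal |
| Battery, baseline and week 12 | Both | Pain, disability, mood, fatigue, quality of life, physical measures | No; indirect signal |
| Weekly yoga log | Both | Time, use of instructions, difficulty, exertion | No |
| Acceptability items | Both | Factors affecting attendance and participation | No; indirect signal |
| Classes, 24 per arm | Both | Contact with an instructor | No reporting role stated |
| Phone numbers | Both | Questions or assistance | Passive; participant must call |
| Invitation to consult instructor | Hatha text only | Problems at home or in class | Invited, not scheduled |
| Contact after unexplained absence | Hatha text only | Reason for absence | Triggered, not scheduled |

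Indirect signals do not record an event, its onset or its setting. A week-12 pain or disability score cannot separate an injury from the ordinary fluctuation of chronic pain, and it is not available for those who have left by then.

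**2. Illustration of what unequal capture would do**

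From the documents: 50 randomised, so n = 25 per arm if balanced (the synopsis in Section 5 says 60; the ratio and the missed share below do not depend on n). Assumed: the same true risk p in both arms (10%, 20% or 30%) and capture probabilities c_H for hatha and c_R for restorative.

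- Expected recorded participants = n × p × c
- Artificial ratio = c_H / c_R
- Share missed overall = 1 − (c_H + c_R)/2

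| c_H, c_R | p = 10% | p = 20% | p = 30% | Ratio | Missed |
|---|---|---|---|---|---|
| 80%, 80% | 2.0 v 2.0 | 4.0 v 4.0 | 6.0 v 6.0 | 1.0 | 20% |
| 80%, 60% | 2.0 v 1.5 | 4.0 v 3.0 | 6.0 v 4.5 | 1.33 | 30% |
| 80%, 40% | 2.0 v 1.0 | 4.0 v 2.0 | 6.0 v 3.0 | 2.0 | 40% |
| 60%, 30% | 1.5 v 0.75 | 3.0 v 1.5 | 4.5 v 2.25 | 2.0 | 55% |

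Example: 25 × 0.20 × 0.80 = 4.0 against 25 × 0.20 × 0.40 = 2.0, and 1 − (0.80 + 0.40)/2 = 0.40.

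The chance that the restorative arm records nobody is (1 − p × c_R)^25. At p = 20% and c_R = 40% this is 0.92^25 = 12.4%, against 0.80^25 = 0.4% with full capture.

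The general lesson does not depend on the inputs. With equal true risk, the recorded ratio is simply the ratio of capture probabilities, and equal capture returns it to 1 at any true rate.

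**The case against.** The strongest case against this point has four parts.

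- **The forms are not in the file.** The self-reports and the log are only summarised. A reader might infer that the instruments contain no adverse event item. The documents do not support that; they support only that none is described.
- **The study is not blind to harm.** Pain, disability and the Neck Disability Index are collected at week 12 in both arms, medication and treatment changes are collected three times, and the acceptability items could pick up a harm-related dropout. Everyone has the phone numbers, and class contact is equal. In the hatha arm the contact after an unexplained absence is not started by the participant, so detection there does not rest wholly on volunteered complaints. All of this stands, and it limits the claim to likely under-counting, since these signals are indirect or passive.
- **The difference between arms is unproven.** A reader might infer that the arms will be handled differently. The hatha text is long because its manual already exists; the restorative manual is yet to be written and may contain the same provisions. Section 15 makes no distinction by arm. What stands is a gap in the written plan, not a demonstrated difference in conduct.
- **The consequence is modest.** Aims 4 to 6 concern recruitment, adherence and effect size, and no comparison of harms between arms is planned. The IMC is to review the protocol before activation and write its own plan, where collection of events could be specified. That is fair. But the IMC plan is not described as covering this, and what goes on participants' forms is best settled in the protocol.

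**Conclusion.** The point holds in a limited form. The plan does not say how adverse events are elicited, and no scheduled contact, as described, asks about them. Non-serious harms are therefore likely to be under-counted in both arms, which would make both look safer. They may also be captured unequally. If the text is followed as it stands, the likelier direction is more events recorded in hatha, so that hatha looks worse than restorative yoga for a reason unrelated to risk.

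The size is unknown. The doubling and the 40% missed share come entirely from assumed capture rates and are not estimates for this trial. A statement that harms will be under-counted, or will be counted differently by arm, goes beyond the documents. The conclusion assumes that the summaries of the forms are complete and that the restorative manual adds nothing to the current text. This is a worthwhile, inexpensive improvement, not a flaw that invalidates the pilot.

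**What to change.** 1. Add one adverse event question, worded identically in both arms, to the existing week 4, 8 and 12 self-reports: any new injury or worsening of symptoms since the last contact, with onset, setting (class, home or assessment) and care sought.
2. Collect those self-reports from everyone randomised, and say explicitly that this includes people who stop attending.
3. Write the instructor-consultation and missed-session contact procedures for both arms, and state that problems learned this way are passed to the study team.
4. Add to the statistical section a table of solicited adverse events by arm.

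An item on the weekly log and a same-day reporting rule for instructors are optional additions.

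The cost is a few items on forms already planned and a few lines in manuals, one set of which is still to be written. No new visits are needed. The downside is that more minor events will be recorded and reported, so the stated harm rate will look slightly less favourable.
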